At their first meeting, the DSMB will discuss the protocol and establish guidelines for study monitoring. The DSMB Chairperson, in consultation with the PI and the NIA Program Officer as needed, will prepare the agenda. Unless otherwise designated by the DSMB, the DSMB Chair will serve as the contact person for unanticipated problem and serious adverse event reporting. Procedures for notifying the Chair of the DSMB and the NIA Program Official of any such events will also be discussed. The format and content of the reports for both the open and closed sessions will be finalized and approved, although additional changes and requests can be addressed throughout the study. At the first meeting, the Board will decide if an interim analysis will take place (e.g. after n participants have been accrued or completed the trial). Interim analyses of efficacy data will only be performed if planned and approved in advance, and when criteria for possible stopping are clearly defined. Well-defined stopping rules will be established during the first DSMB meeting to guide expected causes of termination.

The PI and [name] (study statistician) will be responsible for coordinating activities of the DSMB including the following: 1) Arranging DSMB meetings and communications. 2) Identifying and reviewing open session materials to be presented to the DSMB. DSMB meeting materials to be reviewed by the DSMB members will be prepared by [name] and sent to members at least 7 days before the meeting. Interim data reports will consist of two parts: Part 1 –Open Session Reports (for example, accrual, participant baseline characteristics, adverse events, serious adverse events); and Part 2 - Closed Session Reports.

The Chair of the DSMB will be responsible for the following: 1) developing the meeting agenda; 2) requesting information for the meetings from the PI and the study statistician; 3) overseeing the meetings; 4) verifying that the reports and recommendations prepared are an accurate and complete record of the DSMB's deliberations; 5) serving as contact person for unanticipated problem and serious adverse event reporting.

The DSMB members will 1) familiarize themselves with the research protocol and consent forms, 2) review interim reports of adverse events, 3) review interim analyses of outcome data as it relates to safety, 4) review interim reports of trial participant accrual, and 5) make recommendations to the investigators concerning continuation,

termination, or modification of the trial.

Between meetings of the DSMB and throughout the course of the trial, information regarding issues deemed critical to the trial or to the safety of research participants will be provided to the Chair of the DSMB and the Program Officer by the PI.

A formal report containing the recommendations for continuation or modifications of the study will be prepared by the DSMB Chairperson. This draft report will be sent to the DSMB members within 7 days after the meeting. Once approved by the DSMB members, and no later than 2 weeks after the DSMB meeting, the DSMB Chair will forward the formal DSMB recommendation to the NIA Program Officer and PI. It is the responsibility of the PI to distribute the DSMB recommendation to all co-investigators and to ensure that copies are submitted to all the IRBs associated with the study when necessary.

If study termination is ever considered by the DSMB, the full vote of the DSMB will be required. A recommendation to terminate the study will be made by a majority vote. The DSMB Chair will provide the tiebreaking vote in the event of a 50-50 split vote. In the event of a majority vote for continuation with at least one vote for study termination, a written statement with accompanying reasons for the vote(s) to terminate should be contained within the report issued by the DSMB. In the event of a recommendation to modify the protocol or to terminate the study, the PI may disagree with the recommendation of the DSMB. If the PI does not concur with the recommendation of the DSMB. If the PI does not concur with the recommendation of the DSMB, then the IRB, the institution official, and the funding agency must be notified in writing of this disagreement and the reason for it. The PI may appeal the decision and offer an alternative to termination or study modification for consideration by the DSMB. If an impasse is reached, the appeal will be forwarded to the Chair of the Institutional IRB who will review the case under advisement from the PI and the Chair of the DSMB and will recommend a course of action. This course of action will be recorded by the DSMB and the NIA Program Officer.

If no, please justify why not.

Is there a Data Safety Monitoring Plan (DSMP)?

Y

If yes, describe the data and safety monitoring plan developed to ensure the safety of participants and the validity and integrity of research data. Monitoring should be commensurate with risks and with the size and complexity of the trials. As such, state that SAEs will be reviewed by a qualified MD in real time and indicate how often aggregate data will be reviewed for safety trends.

Data and Safety Monitoring Plan

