In the telephone appointment, the study staff member will provide information about the study and will screen for capacity to consent by assessing the following. Does the resident respond appropriately to a social greeting? Is the resident oriented to place? Does the resident understand who the study team member is after the team member explains their identity? During the course of this introductory conversation, was the resident able to respond fluently and socially appropriately? If so, the team member will go through the consent form with them. Residents will then be asked a series of questions to assure their understanding. These questions are as follows: Describe in your own words what this study is about? Describe what I am asking you to do to participate in this study? Are you required to do this interview with me?

What will happen if you don't talk to me? What happens if you decide you don't want to participate once we get started? What will I do with the information you give me?

The NH leadership team member will support this telephone conversation by assuring that the resident has a quiet environment to have the telephone conversation and that the resident has in front of them a printed large-font version of the ICF written in first person with the signature area flagged. If the resident is able to respond appropriately to all the capacity screening questions, and they do wish to participate, then the resident will be instructed to sign the ICF. The study staff person will contact the NH leadership team member and ask them to make a copy of the ICF for the resident to keep, place a copy in the medical chart, and express mail the original to the UA study office using a provided pre-paid envelope. If the resident is able to respond appropriately to all the capacity screening questions and does not wish to participate then they will not be enrolled in the study, regardless of the LAR's consent. In this case, the study team member will let the NH leadership team and the LAR know that the resident has declined participation.

Under all circumstances, the NH resident's autonomy will be respected. For NH residents without capacity to consent, their assent to participate will be obtained whenever possible, and their decision to withdraw at any time (whether expressed verbally or by resistance to participation) will be honored (see also staff training in Section #3B-Study Procedures).

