The most likely cause of resident unwillingness to continue participation would be over the wearing of the actigraph and/or fitbit. NH staff will be trained by their NH leadership teams or their trained designees (who will have been trained by [name] or her study team designees) on proper use and placement of actigraphs and Fitbits, verbal and behavioral signs of

distress that might indicate actigraph/Fitbit-related discomfort/distress [e.g., verbal indicators such as words (e.g., "take it off!"), distress sounds (e.g., crying, moaning, groaning), physical movements (e.g., picking at the device, shaking the arm)], and appropriate modification techniques to try to relieve such distress. NH staff will be informed that the devices should be removed in the unlikely event that distress behaviors are not relieved by modification techniques. NH staff will be trained on importance of NH resident autonomy, and will be engaged in a discussion of how to assess for and honor NH

resident assent or lack thereof with regard to the devices.

b) Describe what provisions are in place to protect the participants' rights in the event they lose their capacity to consent or their capacity to withdraw during the course of the research. (e.g., power of attorney, consent a caregiver as well as the patient, etc.).

Most residents will not have the capacity to consent. As described above, behavioral indicators of withdraw of assent will be honored and NH staff will be carefully trained to recognize these indicators. In addition, LARs will have the study team's contact information and a copy of their consent form which clearly indicates how they can reach the study team and withdrawn consent at any time. These procedures will be reviewed with LARs as part of the consent process.

c) Describe what provisions are in place for use of additional waiting periods to allow potential participants time to consult with family members about whether or not to participate.

Most residents will not have the capacity to consent, and LARs will be consenting. LARs will always be contacted about potential participation before the NH resident is contacted. As described above, if it becomes apparent that the NH resident is able to consent for themselves, their decision will be honored even if it is discrepant from that of the LAR (i.e., if LAR says yes but resident decides no).

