4. Explain how you will identify who is authorized to give legally valid consent on behalf of any individual(s) determined to be incapable of consenting on their own behalf.

We will be guided by the medical chart documentation of who is identified as the legally authorized representative (LAR), combined with guidance from the nursing home staff who know the NH resident and family the best regarding who is the appropriate LAR.

5. Explain the criteria you will use for determining when assent is required for participants who are not competent.

We will always look for assent for participants who are not competent to consent. The behavioral indicators of lack of assent for the actigraph/fitbit are described above.

There are no study self-report data collected from residents. All resident data involved in this study are data that the NH collects as part of their standard clinical practices (e.g., Minimum Data Set (MDS) data that is mandated data collected as per Medicare/Medicaid reimbursement rules). All other resident involvement is concordant with clinical best practice. The main focus of the intervention is with staff behavior. Staff will be implementing interventions that are considered good standard clinical practice, such as providing meaningful activities during the day to help reduce resident daytime napping and reducing noise and resident interruptions at night to promote uninterrupted sleep.

6. Explain what methods will be used for evaluating dissent (e.g., description of behaviors

that would indicate individual does not want to participate (such as moving away, certain facial expressions, head movements, etc...).

Verbal and behavioral signs of distress that might indicate actigraph/Fitbit-related discomfort/distress include: verbal indicators such as words (e.g., "take it off!"), distress sounds (e.g., crying, moaning, groaning), and physical movements (e.g., picking at the device, shaking the arm)].

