Three states are involved – Colorado, South Carolina, and Texas. The definitions of Legally Authorized Representative and decisionally-impaired person for these states are consistent with those used in Alabama as described in the definitions section below (i.e., Alabama law does not specify who may make such decisions. UA legal counsel recommends the following in this order of preference: A legally appointed guardian, a health care proxy or person authorized to make medical decisions in conjunction with a durable power of attorney, a spouse, an adult child, next of kin, or a person or agency acting in loco parentis).

References:

Colorado: https://casetext.com/statute/colorado-revised-statutes/title-15-probate-trustsand-fiduciaries/declarations-future-medical-treatment/article-185-proxy-and-surrogatedecision-makers-for-medical-treatment-and-for-health-care-benefit-decisions South Carolina: https://www.palmettohealthfoundation.org/documentlibrary/research/policies-pgrs Texas: https://www.uthscsa.edu/sites/default/files/Services/forms/irbconsentpolicyattachment1.p df

Definitions:

Assent - is defined as a child's or decisionally-challenged individual's affirmative agreement to participate in research. Mere failure to object should not, absent affirmative agreement, be construed as assent.

Competence "Technically, a legal term, used to denote capacity to act on one's own behalf; the ability to understand information presented, to appreciate the consequences of acting (or not acting) on that information, and to make a choice." [OHRP Institutional Review Board Guidebook, Chapter VI, Section D]

Permission is defined as the agreement of parent(s) or guardian to the participation of their child or ward in research or clinical investigation. Permission includes the element of consent set forth in federal regulations and outlined in the informed consent template included in the IRB expedited and full review applications.

In Alabama child/children refers to all individuals less than 18 years of age unless the individual(s) is/are legally emancipated. (See Guidance: Alabama Law on Children, Minors, Consent, and Other Research-Related Topics. Individuals less than 18 years of age who are not emancipated meet the federal definition for "child" (e.g., Department of Health and Human Services (DHHS), Food and Drug Administration (FDA), and U.S. Department of Education).

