NH leadership team training: The NH leadership team will complete NIH-required computer-based trainings (on the protection of human research participants, HIPAA, and Good Clinical Principles). Study staff will also provide a 2-hour training on procedures to protect vulnerable subjects, as follows: proper procedure for, and importance of only using IRB-approved procedures and letters when sending study opt-out letters to LARs; proper procedures for maintaining security and privacy of data packages mailed to the University of Alabama project office; proper procedures for avoiding coercion or appearance of coercion of research participation when working with NH staff (e.g., not asking staff about research interview participation); proper procedures for assisting in telephone appointment arrangements and providing logistical support when study team members conduct telephone-based NH resident consenting and capacity to consent assessment; importance of only study team members conducting actual consent procedures of anyone (LARs, NH residents, NH staff);

importance of only properly trained NH leadership team members participating in study procedures. [name] (via zoom teleconference) will work together to provide training on the appropriate application of actigraphs and Fitbits to promote comfort and prevent adverse experiences, as well as appropriate assessment equipment maintenance and data mailing.

NH staff training: As part of the intervention training, NH staff will be trained by their NH leadership teams or their trained designees on proper use and placement of actigraphs and Fitbits, verbal and behavioral signs of distress that might indicate actigraph/Fitbit-related discomfort/distress, and appropriate modification techniques to try to relieve such distress. NH staff will be informed that the devices should be removed in the unlikely event that distress behaviors are not relieved by modification techniques. NH staff will be trained on importance of NH resident autonomy, and will be engaged in a discussion of how to assess for and honor NH resident assent or lack thereof with regard to the devices.

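### The same resident behaviours are listed as signs of dissent and as device distress to be relieved first, and the protocol does not say which instruction applies

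*Combined protocol and SAP*

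**What the plan says.** All references are to the combined protocol (the IRB application).

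- **Withdrawal promise.** Section 7(n), Section 2, item 2, Step 2 says of residents without capacity that "their decision to withdraw at any time (whether expressed verbally or by resistance to participation) will be honored". The monitoring plan (8b, 1.3.a) and section 12 repeat this. Item 3(b) adds that behavioural indicators of withdrawn assent will be honoured. Section 8, item 7 gives residents and their legally authorized representatives (LARs) a right to refuse the actigraphs and Fitbits.
- **Signs of dissent.** The prompt for item 6 begins "6. Explain what methods will be used for evaluating dissent". The answer begins "Verbal and behavioral signs of distress that might indicate actigraph/Fitbit-related discomfort/distress include: verbal indicators such as words" and goes on to a spoken demand to take the device off, crying or moaning, picking at the device and shaking the arm. Item 5 says the indicators of lack of assent for the devices are those already described, which is the list in item 3(a).
- **Staff instruction.** Item 3(a) gives that list as signs of device distress, says staff will be trained in modification techniques, and continues: "NH staff will be informed that the devices should be removed in the unlikely event that distress behaviors are not relieved by modification techniques". Section 3(b) (training given by the trained trainers) and 8b, 1.3.b repeat the rule. Section 8, item 5 and 8b, 1.1 give a similar sequence for significant behavioural distress: modifications and alternatives, then discontinuation if the distress does not subside.
- **Softening text.** The sentence after the removal rule says staff will discuss how to assess and honour a resident's assent, or its absence, to the devices.
- **Definition.** Section 7(n), Section 4 defines assent as affirmative agreement and adds: "Mere failure to object should not, absent affirmative agreement, be construed as assent".

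**The concern.** A nurse who hears a resident say *take it off!* has two written instructions. One treats the words as dissent, which is to be honoured. The other treats them as distress, to be met with modification and then removal if that does not work. Nothing tells the nurse how to choose.

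The written rule carries more weight here than in most studies. Item 3(a) names device wear as the most likely cause of unwillingness to continue and provides no re-consent. Item 3(b) says most residents will lack capacity. Research staff will not enter the homes, and device training reaches frontline staff through the home's own leadership and implementation teams (section 3(b)).

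There is also a consequence for what the pilot learns. Section 3(b) makes it a condition for considering Fitbits in the R33 trial that staff and residents consistently find two devices at once acceptable. Section 3(d) bases that decision on staff interviews and plans no count of resident refusals.

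**Working it through.** No formula applies, so the check sets the passages side by side.

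| Question | Dissent and withdrawal text | Device-handling text |
|---|---|---|
| What are the signs? | 7(n) item 6, and item 5 by reference back: spoken demand, distress sounds, picking, arm shaking | 7(n) item 3(a): the same list |
| What are they called? | Dissent, or lack of assent | Discomfort or distress |
| What follows? | Withdrawal is honoured at any time (item 2, Step 2; item 3(b)) | Modification, then removal if not relieved (item 3(a); 3(b); 8b, 1.3.b) |

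1. **Is it one list?** Yes. Item 6 reproduces the categories and examples of item 3(a), and item 5 points back to them.
2. **Do the two instructions lead to different actions?** They can. If a spoken demand is followed by an adjustment and the resident then settles, the device rule is satisfied and the device stays on. Under the withdrawal promise, the same words may already have been a decision to withdraw.
3. **Is there a tie-break?** None was found. The withdrawal promise in item 2 cross-refers to the staff training in section 3(b), and its repeat in 8b, 1.3.a cross-refers to 1.3.b. Both training texts contain the modify-then-remove rule. The cross-reference therefore leads from the promise back to the instruction that conflicts with it.
4. **Is affirmative agreement sought?** Item 2 says assent will be obtained whenever possible, and item 5 says it will always be looked for. Item 5 then describes only signs of its absence. No passage says how affirmative agreement to the devices, as the definition requires, is asked for or recorded.
5. **How often could the question arise?** Three measurement periods × 7 days = 21 nights per resident, with two devices. Leadership-team training in section 3(b) describes removal in the morning, which implies up to 21 fittings. For the 57 residents anticipated, 57 × 21 = 1,197 resident-nights at most. This is exposure, not a count of objections. The documents give no refusal rate.

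**The case against.** The strongest reply is that the documents show which principle governs. The withdrawal promise is introduced by a statement that the resident's autonomy will be respected under all circumstances. Item 3(b) repeats the promise directly after the device instruction, and the training sentence on honouring assent is specific to the devices. Modification is also a sensible response to a tight strap. The terms modification and alternatives are undefined and could include taking off one of the two devices. This establishes the intent. It does not give staff a rule for sorting the signs, and the one concrete sequence they are given is to modify and then remove.

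It is also fair that only items 3(a) and 6 name the specific signs. Section 3(b) and 8b, 1.3.b refer to distress signs generally, and section 8, item 5 and 8b, 1.1 apply to significant distress. Training materials and attached forms are not in the text reviewed and may draw the distinction.

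A reader might infer four stronger points that the documents do not support:

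- *That this instruction is a resident's only way to refuse.* LARs can withdraw consent at any time (item 3(b)), and residents and LARs may refuse the devices (section 8, item 7).
- *That missing-data rates would be biased.* A night on which the device was worn after re-fitting is truly not missing, and section 3(d) plans no refusal rate that could be distorted.
- *That under-recorded refusal can be quantified.* No figure in the documents supports an estimate.
- *That the definition of assent is plainly breached.* It states what assent is, not what to do after an objection, and item 5 does not equate assent with silence. The gap is that no method of seeking agreement is described.

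**Conclusion.** The concern holds as an internal conflict in the operating instructions. One list of signs serves as evidence of dissent and as a trigger for modification, and no passage gives precedence or separates the two uses. The instruction, followed as written, can override a listed sign of dissent. The link to the definition of assent is secondary and rests on inference.

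No sample size, estimate or test in the plan depends on this. It matters for the protection of residents without capacity, and for the evidence behind the two-device criterion, which as planned rests on staff impressions. The conclusion assumes that the unseen training materials and forms do not already draw the distinction or record refusals. If they do, the protocol need only say so. Which signs belong in which group is for the investigators and the IRB to settle.

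**What to change.** 1. Reconcile the device instruction (section 3(b) trained-trainer text; 7(n) item 3(a); section 8, item 5; 8b, 1.1 and 1.3.b) with the withdrawal promise, the answers to items 5 and 6, and the definition of assent. The result should state which signs are handled as withdrawal and which as discomfort, consistently with the promise, and how affirmative agreement to the devices is sought.
2. Add one line to the staff sleep report, already kept in weeks 1, 8 and 15, recording device refusals separately from discomfort adjustments or removals.
3. In section 3(d), report these counts alongside the staff-interview findings, so that the Fitbit decision has resident-level evidence.

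The cost is a revised data sheet, which means changing a form already submitted to the IRB, and one added training point. There may be somewhat fewer device nights.
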